4.2 Planned analyses

- 4.2.1 Interim analyses for Adaptive sample size reassessment
- 4.2.2 Two interim analyses at half and three-quarter information time (i.e. when half and three-quarter of the subjects are evaluable for response), using O'Brien-Fleming boundaries for efficacy and futility.

A Data Safety Monitoring Board will be settled by the sponsor and will be composed of experts in mechanical ventilation independent from the study coordinators and investigators.

The responsibility of the DSMB is to evaluate safety data during the trial and to advise Hamilton Medical about the continuing safety of the Study. Tables, listings and figures to be presented during each DSMB meeting are listed in the DSMB Charter. However, additional items can be added upon request from DSMB members.

Listings of all Adverse Events and Device Deficiencies will be provided by Hamilton Medical to the Independent Medical Monitor to evaluate safety of the study device. All events, including any device related events will be reviewed case by case by the Independent Medical Monitor. A safety concern raised by the Independent Medical Monitor triggers a DSMB meeting. Trial data will be reviewed on a periodic basis as defined in the DSMB Charter.

Based on the available safety data, the DSMB may recommend that Hamilton Medical modify or terminate the trial. DSMB composition, duties, procedures, deliberation rules are detailed and documented in the DSMB Charter.

4.2.3 Final Analysis

The final analysis will be performed when the last subject has been followed at the end of the study. Accrual is expected to be completed in approximately 24 months.

4.3 Definition of Populations

This study will enrol adult ICU subjects, 21 years and older, requiring invasive mechanical ventilation and meeting the inclusion and exclusion criteria. Inclusion and exclusion criteria are detailed in Sections 7.2 and 7.3 of the protocol respectively.

4.3.1 Intention-To-Treat (ITT) Population

The Intention-To-Treat population (ITT) will consist of all randomized subjects. Subjects who receive the wrong ventilation support will be analysed in the arm to which they were randomized. The ITT population will be used for primary, secondary, and tertiary efficacy analyses.

4.3.2 Modified Intention-To-Treat (MITT) Population

The MITT population consists of all ITT subjects whose recorded data are at least 24h and at least 80% of the invasive ventilation duration within the allocated randomized ventilation mode is recorded in the eCRF. The sensitivity analyses for efficacy endpoints will be conducted using the MITT population. Subjects will be analyzed in the group to which they were randomized.

4.3.3 Safety Analysis Population

The Safety population will include all subjects who once received invasive mechanical ventilation. Subjects will be analyzed according to the ventilation mode that they received. The safety population will be used for safety analyses.

4.4 Subgroup Definitions

Forest plots will be used to display results of primary endpoints and total duration of MV within the following subgroups listed below:

- Regions (US vs Europe)
- Study centers
- Gender

All efficacy tables and forest plots displaying primary and tertiary efficacy results will also be presented by treatment arm and for four groups based on subject condition at inclusion:

- Normal lungs
- ARDS
- Chronic Hypercapnia
- Brain injury

Additionally, forest plots to display primary and tertiary efficacy results by spontaneous and passive breathing subjects for the six ventilation and oxygenation variables will be reported:

1) Tidal volume (VT)

- 2) Maximum pressure (Pmax)
- 3) Oxygen saturation measured by pulse oximetry (SpO₂)
- 4) End-tidal partial pressure of carbon dioxide (PetCO₂)
- 5) Respiratory rate (RR) for spontaneous breathing subjects
- 6) Pmax-PEEP for passive ARDS subjects

Study centers will be pooled from largest to smallest until the pooled center had more than 5 subjects in each treatment group.

4.5 Treatment Assignment and Treatment Arms

The two ventilation arms are:

- Automated ventilation arm: INTELLiVENT-ASV software accessory will be activated, utilizing a Hamilton-Medical Ventilator
- Non automated ventilation arm: INTELLiVENT-ASV software accessory won't be activated

4.6 Calculated Variables

- Study day 0 is defined as the first day when study ventilation period starts.
- Baseline assessments done on the date of ventilation are assumed to take place before the study ventilation period starts, unless specified otherwise.
- Event durations in days (e.g., AE duration) are calculated as follows: [end date start date +1]. When applicable, Time durations in hours are calculated as follows: [end time start time]

4.7 Partial Dates

If part of the starting or ending dates of an adverse event (AE) is missing, the following convention will be used:

- For a missing day in an AE 'start date', the missing day is replaced by the first day of the month (e.g., UKMAY2020 -> 01MAY2020)
- For a missing day in an AE 'end date', the missing day is replaced by the last day of the month (e.g., UKMAR2020 -> 31MAR2020)

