8.1.2 Point of Enrollment and Randomization:

Subjects or next-of-kind or a legally authorized representative who sign and date the ICF and meet all of the study eligibility criteria will be eligible for inclusion into the EASiVENT Study.

Two different scenarios might occur:

1. The patient is already under invasive ventilation (intubated) for less than 24 hours, the next-of-kind or a legally authorized representative will sign and date the ICF.
2. The patient is able to sign and date the ICF before intubation.

The subject will only be considered enrolled when the **ICF signed and dated** and the subject will be **randomly assigned (1:1)** to automate ventilation with INTELLiVENT-ASV or to the non-automated ventilation.

Randomization will be stratified according to the clinical condition at inclusion (normal lungs, ARDS, chronic hypercapnia, brain injury). According to randomization allocation, the subject's attending physician will adjust the ventilator settings and recording will start.

Recording of ventilation data will start as randomization is completed and allocated randomization mode is selected.

Enrolled subjects will be documented on the Screening and Enrollment Log.

The investigator will maintain a log of all subjects screened and enrolled in the clinical study, assigning an identification code linked to their names, alternative subject identification or contact information. Patients who do not qualify for enrollment will be documented as ineligible on the Screening and Enrollment log.

Adverse Event collection will be started after point of enrollment.

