9.1.2 Adverse Events (AEs)

ISO 14155 / MDR 2017/745 Definition (regulatory definition):

An AE is any untoward medical occurrence, unintended disease or injury or any untoward clinical signs, (including an abnormal laboratory finding,) in subjects, users or other persons, in the context of a clinica investigation, whether or not related to the investigational medical device. and whether anticipated or unanticipated.

NOTE 1 to entry: This definition includes events related to the investigational medical device or the comparator.

NOTE 2 to entry: This definition includes events related to the procedures involved.

NOTE 3 to entry: For users or other persons, this definition is restricted to events related to investigational medical devices.

Specificities to EASiVENT:

The following Adverse Events (**AEs**) **will be recorded during** the EASiVENT Study Days 0 through 28:

1. Serious Adverse Events (SAEs) other than those listed as study-specific outcomes
2. Non-serious AEs that are considered by the investigator to be possibly, probably, or definitely (causally) related to mechanical ventilation as a supportive measure for acute respiratory failure.
For details please refer to EASiVENT Study list of Adverse Event, [Annex D](#)
3. AEs that lead to permanent discontinuation of INTELLiVENT-ASV-Management.

Investigators will be instructed to record their assessment of the potential relatedness of each Adverse Event (AE) to protocol procedures and mechanical ventilation. Potential relatedness of an event to mechanical ventilation will be determined by evaluating the temporal relationship and if the event is unanticipated or unexplained given the patient's clinical course, care, and previous medical conditions. The degree of certainty the investigator has regarding relatedness of the event to mechanical ventilation will be recorded as not related, possibly related, probably related, or definitely (causal) related. If patient's INTELLiVENT-ASV-Management is discontinued as a result of an AE, study site personnel will clearly record in the eCRF of the Study the circumstances and data leading to discontinuation of INTELLiVENT-ASV as ventilation mode.

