9.1.3 Serious Adverse Event (SAE)

ISO 14155 / MDR 2017/745 Definition (regulatory definition):

An SAE is any adverse event that led to any of the following:

- a) *led to a death*
- b) *led to a serious deterioration in health of the subject, users or other persons as defined by one or more of that resulted in any of the following:*
 - *a life-threatening illness or injury, or*
 - *a permanent impairment of a body structure or a body function, including chronic diseases, or*
 - *in-subject hospitalization or prolongation of existing patient hospitalization, or*
 - *in medical or surgical intervention to prevent life threatening illness or injury or permanent impairment to a body structure or a body function,*
 - *Chronic disease,*
 - *led to foetal distress, foetal death or a congenital abnormality or birth defect including physical or mental impairment physical or mental impairment or birth defect.*

Specificities to EASiVENT:

SAE recording begins after the patient has signed informed consent and has received INTELLiVENT-ASV or standard of care mechanical ventilation (point of enrollment). If a patient experiences a SAE after signing informed consent, but prior to receiving the study intervention, the event will not be recorded unless the investigator feels the event may have been caused by a study procedure.

SAEs will be collected Day 0 through Day 28 of the study period or until extubation, whichever occurs first. Thereafter, SAEs are not required to be recorded unless the investigator feels the events were possibly, probably, or definitely (causal) related to study procedures.

An SAE is any Adverse Event (AE) that results in one of the following events and is not classified as a study-specific clinical outcome using the definitions enumerated above:

1. Death that is not related to the underlying illness or associated condition or death that is possibly, probably, or definitely (causal) related to study procedures
2. Resuscitated cardiac arrest that is not related to the underlying illness or associated condition, or that is possibly, probably, or definitely (causal) related to study procedures

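### SAP 4.7 imputes partial adverse event dates with no bound at enrolment, death or study exit, so some events get impossible onset or end dates

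*SAP*

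**What the plan says.** SAP 4.7 gives two unconditional rules. For an AE start date, "the missing day is replaced by the first day of the month". For the end: "For a missing day in an AE 'end date', the missing day is replaced by the last day of the month". Neither has an exception for a subject who enrolled, died or left the study during that month.

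SAP 4.6 then uses such dates: "Event durations in days (e.g., AE duration) are calculated as follows", the formula being end date minus start date plus one.

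The collection rules set limits that the imputation does not follow. Protocol 8.1.2 states "Adverse Event collection will be started after point of enrollment". Protocol 9.1.2 records AEs during "the EASiVENT Study Days 0 through 28". For serious events (SAEs), Protocol 9.1.3 states "SAEs will be collected Day 0 through Day 28 of the study period or until extubation, whichever occurs first", with later events recorded only if judged related to study procedures. SAP 4.1.1 limits follow-up to 28 days. Nothing else in either document bounds the imputed dates.

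**The concern.** A calendar month is about as long as the whole follow-up, so moving a date to the edge of its month can carry it outside the subject's time in the trial. Take a subject enrolled on 20 May whose event began on 22 May, with the day not recorded. The rule dates the onset 1 May, 19 days before enrolment, although the protocol does not collect AEs from that time. The end rule has the mirror fault: a month-end date can fall after death or after Day 28.

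At stake are the dates shown in AE, SAE and death listings if imputed dates are printed, the AE duration that SAP 4.6 defines, and any program that applies the 28-day SAE window of SAP 8.3 by date. The SAP does not say how an event with a negative study day should be handled.

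**Working it through.** The documents give no figure on this point, so there is none to reproduce.

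**Inputs**
- Imputation rules: SAP 4.7. Duration formula: SAP 4.6.
- Earliest onset is enrolment (Protocol 8.1.2); AE window Days 0-28 (Protocol 9.1.2).
- Enrolment calendar: planned Q4 2020 to Q4 2022 (protocol synopsis). *Assumption:* enrolment uniform over the calendar days from 1 October 2020 to 31 December 2022.
- Day of onset: not in the documents. *Assumption:* a range of patterns.

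**Start date.** Let onset be on study day k and on day d of the month. The imputed start is d − 1 days before the true onset, so it precedes enrolment exactly when d − 1 > k. With mean month length L = 365/12 = 30.4 and d roughly uniform,

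P(start before enrolment) ≈ (L − 1 − k)/L.

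This is linear in k, so for a uniform onset window the mean k can be used:
- Days 0-28, mean k = 14: (30.4 − 1 − 14)/30.4 = 15.4/30.4 = 51%.
- Days 0-7, mean k = 3.5: (30.4 − 1 − 3.5)/30.4 = 25.9/30.4 = 85%.

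The mean backward shift is (L − 1)/2 = 29.4/2 = 14.7 days, whatever the onset pattern.

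**End date.** If the event ends in its onset month, the imputed end falls after Day 28 when the days left in the month exceed 28 − k:

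P(end after Day 28) ≈ (L − 29 + k)/L.

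- Days 0-7: (30.4 − 29 + 3.5)/30.4 = 4.9/30.4 = 16%.
- Days 0-28: 15.4/30.4 = 51%.

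**Exact enumeration over the calendar.** The last column is the mean backward shift if the start is not allowed before enrolment.

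| Onset pattern | Start before enrolment | Onset-month end after Day 28 | Mean days moved back | Same, bounded at enrolment |
|---|---|---|---|---|
| Uniform Days 0-2 | 93% | 8% | 14.7 | 1.0 |
| Uniform Days 0-7 | 85% | 16% | 14.7 | 3.2 |
| Uniform Days 0-14 | 74% | 28% | 14.7 | 5.8 |
| Uniform Days 0-28 | 51% | 51% | 14.7 | 9.4 |
| Uniform Days 14-28 | 28% | 74% | 14.7 | 13.1 |

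For a single onset day, the share of starts dated before enrolment is 97% at Day 0, 51% at Day 14, 47% at Day 15, 28% at Day 21 and 5% at Day 28.

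**Duration.** With both days missing, the SAP 4.6 formula returns at least a full calendar month, 28 to 31 days, even for an event that lasted hours.

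**The case against.** The strongest reply is that this is a programming convention with no shown effect on a planned result. Much of that stands.

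- *Are events lost?* A reader might infer that an SAE with a negative study day drops out of the secondary safety endpoint. No written rule does this. Inclusion is settled at collection, and SAP 8.3 and 8.5 tabulate recorded events with no date filter.
- *Are events reclassified?* A reader might infer that a pre-enrolment date makes an event look pre-existing and unrelated. Under Protocol 9.1.2 the investigator judges relatedness, and the medical monitor and DSMB assess it independently. SAP 4.8 treats a missing relationship as possibly related. No step uses an imputed date.
- *Are reported durations inflated?* AE duration appears in SAP 4.6 only as an example, and the output lists in SAP section 10 contain no AE-duration or time-to-onset table. The SAP does not say whether listings print raw or imputed dates.
- *Is it common?* Probably not. Protocol Table 1 schedules visits about once or twice a day, Protocol 9.3 has AEs screened twice a day, Table 4 requires SAEs within three calendar days of the site learning of them, and section 11.2.1 provides automatic queries.

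The reply does not remove the contradiction. The SAP states a rule that yields dates its own protocol excludes. A simple cap at Day 28 would be a poor remedy, because it could override a recorded month.

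**Conclusion.** The point holds as a minor one. The rule in SAP 4.7 conflicts with the start of AE collection and with the length of follow-up. Between 51% (onset uniform over Days 0-28) and 85% (Days 0-7) of partial starts would be dated before enrolment. The onset-month end would fall after Day 28 in 51% and 16% of cases respectively.

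These figures are conditional on a missing day. They assume uniform enrolment and, for the end date, an event that ends in the month it began. Early onset is the more plausible pattern for SAEs, since routine collection stops at extubation and Protocol Annex A, Table 10 gives 2-8 days of ventilation. The documents give no onset distribution, however, and for onsets after Day 14 the affected share is below half. It would therefore be too strong to say without qualification that imputed starts usually precede enrolment.

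The number of partial dates is not stated and is probably small. The effect is confined to listing dates, the derived duration and any date-based use of the 28-day SAE window. The primary analysis and the relatedness assessments are not affected.

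**What to change.** Amend SAP 4.7 as follows.

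- **Start day missing.** If the recorded month and year are those of enrolment, use the enrolment (randomisation) date. For an SAE recorded as occurring before the study intervention, which Protocol 9.1.3 allows in limited cases, use the consent date instead. Otherwise use the 1st.
- **End day missing.** If the recorded month and year are those of death, or of last contact or study exit, use that date. Otherwise use month-end, but never a date after death.
- **Both.** Never override a recorded month or year, and never set the end before the start. A recorded end month later than the month of death should be queried, not imputed.

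The text should name its anchor, because SAP 4.6 counts Day 0 from the start of study ventilation while Protocol 8.1.2 defines enrolment by consent and randomisation.

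For AEs collected after enrolment, the start rule reduces the share of pre-enrolment starts to zero. It cuts the mean shift from 14.7 days to 3.2 (onset Days 0-7) or 9.4 (Days 0-28). The cost is a short paragraph in the SAP and a few lines of code, with no effect on design, sample size or the primary analysis.

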4.8 Methods to be used for handling Missing Data

The subject dataset is considered complete if both of the following conditions are met:

- 1. Minimum of 24h of recorded data available
- 2. Minimum of 80% of the total invasive ventilation time within the allocated randomized ventilation mode has been recorded.

An incomplete dataset leading to a dropout in the study is a dataset that misses at least one of the above-mentioned variables. Subjects for which less than 80% of mechanical ventilation time within the allocated randomized ventilation mode could be recorded due to documented technical reasons, the recorded data (with 'percent spent' calculated per

the recorded time) will be used for the primary analysis of the co-primary endpoints. A maximum of 5% of subjects with less than 80% recorded time is expected. As a sensitivity analysis, these values will be treated as missing data and imputed as described below.

Method that takes into account the presence of missing data and that yield valid estimates under the assumption of data missing at random (MAR) will be used. For the primary analysis, multiple imputation of the missing primary outcome data in both arms will be performed under a missing at random model for the control arm, hence leading to a conservative imputation. The 'percent spent' variables that need to be imputed are continuous-type variables. Those variables will be imputed sequentially using covariates constructed from the corresponding sets of preceding variables, in this case. In addition, should there be any issues with the estimation of the model, the covariates will be prioritized based on the order in which they are listed below.

- Study arm
- Demographic data: Age and gender at Baseline (visit 2)
- Pulmonary condition at visit 1
- History: Cause of ICU admission and patient medical history at baseline (visit 2)
- Intubation status at Visit 5
- ICU severity scores: SAPS II, APACHE and SOFA at visit 5
- Concomitant rescue therapies: Proning, Nitric Oxide at visit 5
- Weaning Information: Active/Passive, NIV, CPAP, weaning process and sedation status at visit 5

Multiple imputation will be used in secondary, tertiary or sensitivity analyses, whenever necessary, to impute the missing data under the MAR assumption.

Missing AE intensities will not be imputed. Such AEs will be included in summaries by including a category of "missing" in the tables. If the assessment of the relationship of the AE to investigational device is missing, we will assume that the AE is possibly related to investigational device.

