5 STUDY ENDPOINTS

5.1 Primary endpoints

Primary endpoints will be measured continuously during ventilation period up to 7 days after enrollment.

Efficacy

Efficacy of the investigational device by assessing the ability to keep ventilation and oxygenation variables in optimal target ranges.

This endpoint will be determined by the percentage of time spent with six (6) variables in the optimal range:

- 1) Tidal volume (VT)
- 2) Maximum pressure (Pmax)
- 3) Oxygen saturation measured by pulse oximetry (SpO₂)
- 4) End-tidal partial pressure of carbon dioxide (PetCO₂)
- 5) Respiratory rate (RR) for spontaneous breathing subjects
- 6) Pmax-PEEP for passive ARDS subjects

The optimal and sub-optimal ranges are defined by pertinent guidelines for different clinical conditions including normal lungs, brain injury, ARDS, and chronic hypercapnia.

Safety:

The primary safety endpoint will be determined by percentage of time spent with at least one variable in the sub-optimal range during the first seven (7) days of enrollment.

For the invasive mechanical ventilation ranges, please refer to section 10.4.5 Analysis of Primary Endpoints.

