7.6 Study Withdrawal

Participants (or spouse/next of kin or legally authorized representative) may voluntarily withdraw from this study for any reason at any time, regardless of the participant retention strategies utilized. Additionally, the IoR may also withdraw participants from the study in order to protect their safety and/or if they are unwilling or unable to comply with required study procedures after consultation with primary investigator and Hamilton Medical. Participants may be withdrawn from the study if the study sponsor, government or regulatory authorities (including Office for Human Research Protections [OHRP] and the FDA) or site IRBs/ECs terminate the study prior to its planned end. Every reasonable effort will be made to complete a final evaluation of participants who withdrawal/terminate early from the study, and study

staff will record the reason(s) for all withdrawals in the participants' study records. In addition, subject withdrawal will be documented in the eCRF on the End of Study forms.

If subjects are transferred after seven (7) days of start of ventilation, primary endpoints will be assessed and study ventilation protocol ended. However, the ventilation duration and mortality will be captured on Day 28 after enrollment via a phone call as described in VFD section.

Dropout could occur when patients are ventilated for less than 24 hours after inclusion because of unexpected death, transfer to another ICU, or withdrawal of informed consent. We expect a maximum of 5% of these cases.

Note a maximum of 5% of subjects are anticipated for which not 80% of mechanical ventilation time, within the allocated randomized ventilation mode, could be recorded due to documented technical reason.

Please refer to: Section 10.5 “Missing Data”

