10.5 Missing Data

Please refer to section 7.2 "Inclusion Criteria" and 8.4 "End of study".

Subject will be considered to have completed the study for the following reasons:

- Subject completes follow-ups (Day 28) required per investigational plan.
- Subject dies.
- Subject or legally authorized representative requests to be withdrawn from the study.
- Investigator requests to be withdrawn from the study to protect the welfare of the subject. (In that case, it is at the site's principal investigator's discretion to determine that the study is no longer in the subject's best interest).

The sponsor deems a dataset "complete" if both of the following conditions are achieved:

1. Minimum of 24h of recorded data available
2. Minimum of 80% of the total invasive ventilation within the allocated randomized ventilation mode time has been recorded.

An incomplete dataset leading to a dropout in the study is a dataset that misses at least one of the above mentioned variables.

The reason for an incomplete dataset can be:

- Early termination of recording caused by a transfer to another ICU
- Subject or legally authorized representative requests to be withdrawn from the study.
- Site's Principal Investigator's decides to stop the inclusion for any reason.
- Technical failure in recording.
- Less than 80% the invasive ventilation within the allocated randomized ventilation mode duration have been recorded in the Memory Box.
- Recorded data is less than 24h.

Dropout could occur when patients are ventilated for less than 24 hours after inclusion because of: unexpected death, transfer to another ICU, or withdrawal of informed consent. We expect a maximum of 5% of these cases.

Note a maximum of 5% of subjects are anticipated for which not 80% of mechanical ventilation time within the allocated randomized ventilation mode could be recorded due to documented technical reason. The recorded data will be used (with 'percent spent' calculated per the recorded time) for the primary analysis of the co-primary endpoints. As a sensitivity analysis, these values will be treated as missing data.

Because technical failure in recording may not be detected on time by the investigators, a continued enrollment is planned.

Technical issue in capturing the necessary data, the dropout probability is assumed to be equal for all subjects, regardless of their condition and ventilation modalities. Therefore, replacing subjects without collected data is not expected to cause any bias.

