3.4.1 Group sequential design with 2 interim analyses

The planned sample size is a minimum of 254 and a maximum of 508 subjects.

The sample sizes for this trial are calculated using the following assumptions:

- significance level equal to 0.025 (1-sided)
- power of 0.8 (at final analysis)
- allocation ratio of 1:1
- Two interim analyses at half and three-quarter information time (i.e. when half and three-quarter of the subjects are evaluable for response), using spending functions with O'Brien-Fleming-Type boundaries for efficacy and futility.
- Efficacy endpoint (%All in optimal, more is better) on logit-scale:
 - Mean conventional = -1.86
 - Mean INTELLiVENT-ASV = -1.28
 - \circ Sd = 1.5 for both devices
- Safety endpoint (%Any in sub-optimal, less is better) on logit-scale:
 - Mean conventional = -0.09
 - Mean INTELLiVENT-ASV = -0.74
 - \circ Sd = 1.6 for both devices
- Correlation between endpoints = -0.85
- Dropout could occur when subjects are ventilated for less than 24 hours after inclusion because of unexpected death, transfer to another ICU or withdrawal of informed consent. A maximum dropout rate of 5% of these cases is expected. Given the large uncertainty on the assumed performance differences and the inclusion of a sample size reassessment, the initial sample size is not increased to deal with this dropout rate. At the second interim the sample size will be re-estimated, taking this observed dropout rate into account.

The table below shows the sample sizes and characteristics of a study with 2 interim analyses, with O'Brien-Flemming boundaries for efficacy and futility. The final sample size for this group sequential design is 254. 254 stands for the number of subjects with evaluable endpoints and means more subjects might have to be enrolled to reach this number. The p-values for significance are increasing at each analysis while the p-value to stop for futility decreases from the first interim analysis to the final analysis. The study has a high probability to stop at the first interim analysis if both ventilation modes have an equal performance.

Sample sizes and operational characteristics for the trial using O'Brien Fleming boundaries for futility and efficacy.

Analysis	SS	Z	Nominal p	α Spend	end Power	
		Efficacy	Efficacy		(Prob stop H _A)	
1 (IA1)	128	2.96	0.0015	0.0015	0.25	

2 (IA2)	192	2.36	0.0093	0.0097	0.
3 (final)	254	2.02	0.0220	0.0250	0
Analysis	SS	Z	Nominal p	Prob Futility Stop	
		Futility	Futility	(Prob stop under H ₀)	

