1 (IA1)	128	0.44	0.3315	0.67	
2 (IA2)	192	1.34	0.0904	0.25	
3 (final)	254	2.02	0.0220	0.06	

Recorded data has to be 24 hours at minimum, and 80% of the invasive ventilation duration have to be recorded in the Memory box. Note that subjects for which less than 80% of mechanical ventilation time could be recorded due to documented technical reasons, the recorded data (with 'percent spent' calculated per the recorded time) will be used for the primary analysis of the co-primary endpoints.

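### The 80% completeness rule is measured over total invasive ventilation in the allocated mode (up to Day 28), while both co-primary endpoints use only Days 0–7

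*SAP*

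**What the plan says.** **Endpoint window.** Protocol 5.1: "Primary endpoints will be measured continuously during ventilation period up to 7 days after enrollment". SAP 3.2.1, 7.1 and 8.2 give the same 7-day window for the efficacy and safety co-primaries.

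**Completeness.** SAP 4.8 sets two conditions: at least 24 h recorded, and "Minimum of 80% of the total invasive ventilation time within the allocated randomized ventilation mode has been recorded". Protocol 10.5 has the same pair. The MITT definitions (SAP 4.3.2, protocol 10.4.3) use the same 80% of invasive ventilation duration in the allocated mode. SAP 3.4.1 gives a looser form without the mode qualifier: "80% of the invasive ventilation duration have to be recorded in the Memory box". The closing paragraph of SAP 4.1.1 also omits the qualifier.

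**How far the denominator can run.** Protocol 8.3.1 (Weaning) lets the ventilator protocols continue to Day 28, and protocol 8.3.4 has breath-by-breath recording for the whole study period.

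**Consequences of failing.** SAP 4.8 treats the dataset as a dropout, and SAP 4.3.2 keeps the subject out of the MITT. If the shortfall has a documented technical cause, the recorded data stay in the primary analysis but are set to missing and imputed in a sensitivity analysis.

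**Transfer.** Protocol 7.6: "If subjects are transferred after seven (7) days of start of ventilation, primary endpoints will be assessed and study ventilation protocol ended". Total ventilation duration is then collected by phone at Day 28. Protocol 10.5 lists this among possible reasons for an incomplete dataset: "Early termination of recording caused by a transfer to another ICU". The SAP does not carry over the sentence from 7.6.

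**The concern.** A completeness rule for an endpoint should measure how much of that endpoint's own window was observed. This one measures something longer. For anyone ventilated beyond Day 7, recording after the endpoint has closed affects whether the 7-day value counts as complete, and good late recording can offset gaps inside the window.

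At stake are MITT membership, the sensitivity analysis that imputes values with under 80% recorded, and the label of dropout. SAP 10.1 also marks the MITT table of the primary efficacy result for production at both interim analyses. The rule probably feeds the count of evaluable subjects behind the 254 and the interim timing as well, although neither document defines evaluable in those terms. For transferred subjects, two programmers could classify the same fully observed 7-day value differently.

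**Working it through.** **The plan's own figure.** The design inputs in SAP 3.4.1 are "significance level equal to 0.025 (1-sided"), "power of 0.8 (at final analysis") and "allocation ratio of 1:1". The logit-scale differences are −1.28 − (−1.86) = 0.58 with SD 1.5 (efficacy) and −0.09 − (−0.74) = 0.65 with SD 1.6 (safety). The endpoint correlation is −0.85.

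- Fixed design, per arm: n = 2 × SD² × (1.960 + 0.842)² / difference².
- Efficacy: 2 × 2.25 × 7.849 / 0.3364 = 105.0, so 210 in total.
- Safety: 2 × 2.56 × 7.849 / 0.4225 = 95.1, rounded up to 96, so 192 in total.
- Simulation of the three looks (128, 192, 254) with the printed boundaries, both endpoints required to cross at the same look, 1,000,000 runs: joint power 0.801, against the planned 0.80.

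The 254 is therefore reproduced. It counts subjects with evaluable endpoints and does not depend on how completeness is defined. The point concerns who is counted, not how many are needed.

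**The 80% rule.** Let T be total invasive ventilation in days, counted from randomisation.

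1. *Full window recorded, nothing afterwards.* The score is 7/T. It reaches 80% only if T ≤ 7/0.8 = 8.75 days.
2. *Recorder fails after Day 7 while study ventilation continues.* With 8 of 14 days recorded, the score is 8/14 = 57%. The primary window is fully observed and the subject fails.
3. *All gaps inside the window, everything later recorded.* The rule tolerates 0.2T days of gaps, so the smallest recorded window that passes is 7 − 0.2T days, a share of (7 − 0.2T)/7.

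| T (days) | Score if only Days 0–7 recorded | Result | Smallest window that passes | Share of window |
|---|---|---|---|---|
| 8 | 7/8 = 87.5% | pass | 5.4 d | 77% |
| 8.75 | 7/8.75 = 80% | pass (limit) | 5.25 d | 75% |
| 10 | 7/10 = 70% | fail | 5.0 d | 71% |
| 14 | 7/14 = 50% | fail | 4.2 d | 60% |
| 21 | 7/21 = 33% | fail | 2.8 d | 40% |
| 28 | 7/28 = 25% | fail | 1.4 d | 20% |

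At T = 28, 1.4 days is 33.6 h, so the 24 h condition is also met.

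**Transfer after Day 7.** Take a subject with the full enrolment-based window recorded, transferred at Day 7 and still ventilated elsewhere. There are two readings of the mode qualifier:

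- It limits the denominator. Study ventilation ends at transfer under protocol 7.6, so the denominator stops there, the score is 7/7 and the subject passes.
- The denominator is all invasive ventilation, with the total known from the Day 28 call. The score is 7/T and the subject fails once T exceeds 8.75 days.

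Neither document chooses. Cases 2 and 3 above do not depend on that choice.

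**With the 80% applied inside the window.** A full 7-day record scores 100% whatever happens later. A subject ventilated through Day 7 needs at least 0.8 × 7 = 5.6 days recorded.

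**The case against.** The strongest defence is that the governing definitions carry the mode qualifier. Recording in the allocated mode starts at randomisation and study ventilation ends at transfer, so a transferred subject can be read as complete. Protocol 7.6 is also the specific rule for that case, while 10.5 only says what the reason for an incomplete dataset can be. This stands: the transfer case is an unreconciled ambiguity, and a reader who infers that every subject transferred after Day 7 becomes a dropout goes beyond the text.

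Other stronger readings are also unsupported:

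- *That the primary analysis discards or imputes observed 7-day values when the shortfall is not technical.* This is inferred from the narrow technical exception. Primary efficacy uses all randomised subjects, and no section says an observed value is removed.
- *That hours before enrolment count against the subject.* This needs the looser wording in SAP 3.4.1 and 4.1.1 together with the intubation clock of a secondary outcome. It justifies a common start point, not a failure rate.
- *That 20% of the window is typical.* It requires 28 days of ventilation with every gap in Days 0–7. Protocol Table 10 gives 2–8 days of mechanical ventilation, and at 8 days the minimum is 77%.
- *That the 24 h floor is part of the same error.* It is a separate choice, stated consistently.

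None of this removes the mismatch, because recorder failure after Day 7 and gaps inside the window produce it on either reading.

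**Conclusion.** The rule is wrong as written for the co-primary endpoints: its denominator is not the endpoint window, and nothing in either document corrects this. A complete 7-day record can fail (57% with 8 of 14 days recorded), and an incomplete one can pass (77% of the window at 8 days of total ventilation, 60% at 14, 20% at 28). The certain effects are on MITT membership, the dropout label and the sensitivity analysis that treats these values as missing. An effect on the evaluable count is likely but not defined. The conflict with protocol 7.6 is conditional on post-transfer time counting and, for recording that stops at Day 7, on total ventilation above 8.75 days.

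The number of subjects affected cannot be derived. The documents give no distribution of ventilation duration, no transfer rate and no rate of recorder failure after Day 7. The anticipated maximum of 5% below the 80% threshold for technical reasons uses the same long denominator, so it does not describe the 7-day window. A reader might also infer bias between arms; that is possible, but nothing in the documents shows or sizes it.

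**What to change.** In SAP 4.8 and 4.3.2 and protocol 10.4.3 and 10.5:

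1. Define completeness for the co-primaries as at least 80% recorded of the invasively ventilated time from randomisation to the earlier of end of study ventilation or Day 7.
2. State that transfer or recorder failure after Day 7 does not affect completeness for the co-primaries, consistent with protocol 7.6, and carry that sentence into the SAP.
3. Use the same start point and wording wherever the rule appears, including SAP 3.4.1 and 4.1.1.
4. Give the tertiary endpoints their own completeness rule over Days 8–28.

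The 24 h condition can stay as it is. The cost is SAP wording, a protocol clarification and a change to the derivation program. Breath-by-breath recording and ventilation start and end times are already planned, so no extra data or subjects are needed and the sample size stays at 254. The change should be made before anyone sees results by arm, because it decides which co-primary values count as complete.
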